## 5. Study Endpoints

Primary endpoint: change in scores on the EXAMINER battery from before to after stimulation.

Secondary endpoints: change in score on the Neurobehavioral Symptom Inventory, Beck Depression Inventory-II, Hamilton Rating Scale for Depression, change in frontal midline theta synchrony on EEG, change in MRI abnormalities, and quality of life measure from time 0 to 1 year.

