Randomization will occur at time of consenting. The study coordinator who consented the patient will use a coin-tossing procedure to determine whether the subject is assigned to the active group (group 1) or control group (group 2). Modifications will be made as necessary toward the end of enrollment to ensure equal group size and balanced distribution of demographic variables such as age and gender. The study coordinator will not be blinded to group assignment, and with the assistance of the Clinical Core, will program the TDCS devices to deliver active or sham stimulation depending on which group the subject has been assigned. However, the coordinator will not be involved in performing any stimulation procedures. The study technician and principle investigator, who will be responsible for administering the stimulation, will not be aware of which group receives active versus control, and will thus be blinded, as the TDCS device will only display the group number (1 or 2).

Once group membership is determined, individual participants may undergo demographic data collection, neuropsychological assessments and tDCS treatment sessions. They may also undergo EEG and/or MRI. Direct identifiers of participants will be maintained on a separate database that will be stored behind locked doors, in a locked filing cabinet in a secure area of the Clinical Core.

**Demographic Data:** As part of the initial assessment, basic demographic data regarding the subject may be noted down, including age, gender, socioeconomic status, educational attainment, handedness, use of common stimulants such as caffeine, and brain injury severity. They may also be asked if they are willing to allow their medical record to be accessed, for the purposes of confirming details about any TBI as well as obtaining results of neuroimaging studies done at the time of injury or afterward. This will include medical, surgical, neurological and psychiatric history, results of lab tests, brain scans, electroencephalography tests, medication lists, information from doctor's visits and hospital visits.

**Neuropsychological testing procedures:** All neuropsychological testing will be administered in the Center for Brain Recovery and Repair Core by trained study personnel under direct supervision of core directors, clinical neuropsychologists Drs. [name], [name], or the PI. The primary dependent outcome variables to be studied are the three composite scores generated by

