Statistical analyses will utilize the CTSC Biostatistics core. Power analyses and statistical analysis strategy were determined with our statistician [name], who will continue to provide recommendations and support throughout the project. Sufficient group sizes were determined on the basis of data derived from preliminary studies. Clark and colleagues found an effect size of Cohen's  $d = 1.2$  for tDCS to induce improvements in cognition. For our power calculations we will assume a more conservative effect size of  $d = 0.7$  which is consistent with a recent meta-analysis of tDCS effect sizes. With 40 tDCS treatment patients compared to 40 sham patients and an effect size of 0.7, we have 80% power to detect effects of active versus sham treatment in a two-sample t-test. Power in the linear mixed model analysis should be superior that that of the t-test. For Aim 1.1, the central analyses evaluate group (active vs. sham) differences in the EEG data and on the three Examiner composite variables across the three initial time points (before, immediately after, and 1 month after tDCS stimulation protocol). To test this hypothesis, three separate linear mixed models analyses will be performed using the three Examiner composite scores (Fluency, Cognitive Control, Working Memory) as dependent variables. In each analysis, we will incorporate three covariates that may predict variation in learning (severity: mild vs. moderate, premorbid intelligence: WTAR score, and symptom burden: NSI). This will allow us to determine predictors of treatment response (Specific Aim 1.3). Sex, ethnicity, and age will also be entered into the statistical model. The effects of these covariates will be estimated by constructing appropriate contrasts in model effects. A similar set of analyses will evaluate group differences on the variables assessed in our long-term oral/phone follow-up (five data points: (1) before tDCS, (2) immediately after tDCS, (3) 1 month post-tDCS, (4) 6 months, and (5) 1 year) for Aim 1.2. For these analyses dependent variables will be the total cognitive items score of the NSI and the PROMIS-29 profile total score). Significant effects will be followed up with more fine-grained analysis of the components of composite scores. The use of linear mixed-models minimizes the adverse impact of a missing data point, which may well occur in a longitudinal clinical study such as this. Expected attrition will be taken into account with an intention-to-treat analysis. Missing data patterns will be analyzed to assess the extent to which they are informative (in contrast to missing at random), and analyses adjusted accordingly. All EEG data will undergo standard preprocessing (e.g. motion correction, spatial normalization) and quality control prior to statistical modeling. Depending on the specific question of the study, data may be analyzed using the general linear model, independent components analysis, machine learning techniques, or a variety of other standard approaches for neuroimaging data.

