multiple opportunities to reconsider any decisions during the screening and consent process, minimizing the possibility of coercion or undue influence by the researchers. If potential participants successfully meet basic study criteria, they will be invited to undergo consent procedures and enrolled in the study. All participants will be fluent in English, and the information contained in the consent form will be discussed with them in addition to their having a written description of the study in the form, to assure that they truly understand the study procedures.

A modified repeated fair coin-tossing randomization procedure will determine group assignment, and modifications will be made as necessary toward the end of enrollment to ensure equal group size. Randomization will occur at time of consenting. The study coordinator who consented the patient will use a coin-tossing procedure to determine whether the subject is assigned to the active group (group 1) or control group (group 2). Modifications will be made as necessary toward the end of enrollment to ensure equal group size and balanced distribution of demographic variables such as age and gender. The study coordinator will not be blinded to group assignment, and with the assistance of the Clinical Core, will program the TDCS devices to deliver active or sham stimulation depending on which group the subject has been assigned. However, the coordinator will not be involved in performing any stimulation procedures. The study technician and principle investigator, who will be responsible for administering the stimulation, will not be aware of which group receives active versus control, and will thus be blinded, as the TDCS device will only display the group number (1 or 2).

Once group membership is determined, individual participants will be scheduled for demographic data collection, neuropsychological assessments, EEG, and tDCS treatment sessions. Direct identifiers of participants will be maintained on a separate database that will be stored behind locked doors, in a locked filing cabinet in a secure area of the Clinical Core.

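### Allocation is made at consent, before the baseline EXAMINER, depression and WTAR testing, so the starting half of the primary change score is collected after the unblinded coordinator knows the arm

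*Combined protocol and SAP*

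**What the plan says.** On timing, Section 10 (Study Procedures, Experimental Design and Methods) states: "Randomization will occur at time of consenting". It then places the baseline work after allocation: "Once group membership is determined, individual participants may undergo demographic data collection, neuropsychological assessments and tDCS treatment sessions", with EEG and MRI as optional additions at the same stage. Section 18 (Recruitment Methods) gives the same order in firmer words: "Once group membership is determined, individual participants will be scheduled for demographic data collection, neuropsychological assessments, EEG, and tDCS treatment sessions".

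On the endpoint, Section 5 reads: "Primary endpoint: change in scores on the EXAMINER battery from before to after stimulation". Section 11 models the three EXAMINER composites over three time points, the first of which is pre-stimulation. It adds as covariates "severity: mild vs. moderate, premorbid intelligence: WTAR score, and symptom burden: NSI".

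On who knows the arm, Section 10 says: "The study coordinator will not be blinded to group assignment, and with the assistance of the Clinical Core, will program the TDCS devices". The only restriction on that person is: "However, the coordinator will not be involved in performing any stimulation procedures". The technician and the principal investigator are stated to be blinded, because the device displays only a group number. Section 7 makes the coordinator responsible for scheduling neuropsychological assessments. It has Core psychometricians administer and score the battery and does not say whether they are blinded.

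**The concern.** A change score has two halves, and an error in the first counts as much as an error in the second. The usual protection is that the baseline is finished before anyone can know the assignment. Here that protection is absent for the primary endpoint and for the two depression scales, which are given verbally and so depend partly on the interviewer.

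Two things are at stake. If knowledge of the arm reaches whoever gives or scores the baseline battery, a baseline recorded slightly low in one arm appears as improvement in that arm with no difference after treatment. Separately, a participant who consents and leaves before testing has already been randomized but has neither a baseline nor an outcome. Intention-to-treat analysis by mixed model keeps people with some observations; it cannot recover someone with none except by assumption.

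**Working it through.** **1. Order of measurement.**

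| Measure | Use | Position relative to allocation |
|---|---|---|
| EXAMINER | Primary endpoint | After (Sections 10 and 18) |
| BDI-II, HAM-D | Secondary endpoints | After: part of the same battery (Section 10, Aim 2.1) |
| WTAR | Model covariate | After: listed in the battery (Section 10) |
| EEG, MRI where done | Secondary endpoints | After (Section 10; EEG also in Section 18) |
| PROMIS-29 | Long-term outcome | Before stimulation (Section 10, Aim 1.2); position relative to allocation not stated |
| NSI | Covariate and secondary endpoint | First given at formal screening, before consent; listed again in the battery |
| GCS, loss of consciousness, amnesia | Basis of severity | Eligibility facts checked at prescreening; severity noted down again at the initial assessment |

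No readable text puts the EXAMINER or depression baseline before allocation. Of the three covariates named in Section 11, only WTAR is firmly post-allocation.

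**2. Who can know the arm.** The person who takes consent also allocates: "The study coordinator who consented the patient will use a coin-tossing procedure to determine whether the subject is assigned to the active group (group 1"; group 2 is control. That coordinator schedules assessments and is kept away from stimulation only. The Clinical Core helps program the devices and also supplies the psychometricians. The blind of the technician and the principal investigator rests on a display of 1 or 2, a code that the protocol itself decodes. Section 10 elsewhere says the stimulator is programmed to randomize, which conflicts with the coin toss, so the route by which the arm becomes known is itself unsettled.

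**3. The plan's own figure, for context.** Section 11 states 80% power for 40 against 40 at d = 0.7 in a two-sample t-test, without giving alpha. At two-sided 0.05, the noncentrality is 0.7 × √(40/2) = 3.13 on 78 df, and power is 87.1%. The stated figure is not reproduced, but it errs on the cautious side and this point does not rest on it.

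**4. Illustration of a differential baseline (assumed inputs).** Take a score with SD 1 at each visit, pre-post correlation ρ, no true effect, and a baseline recorded b lower in the active arm.

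- Change score: δ = b / √(2(1 − ρ)).
- Baseline as covariate: δ = ρb / √(1 − ρ²).
- Rejection rate: two-sided 5% t-test, 78 df, noncentrality δ√(40/2) = 4.472δ (an approximation for the covariate analysis).

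For b = 0.2 and ρ = 0.5, the change score has δ = 0.2 / 1 = 0.2, noncentrality 0.894 and rejection 14.3%. With the covariate, δ = 0.1 / 0.866 = 0.115, noncentrality 0.516 and rejection 8.0%.

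| ρ | Analysis | b = 0.1 | b = 0.2 | b = 0.3 |
|---|---|---|---|---|
| 0.5 | Change score | 7.3% | 14.3% | 26.3% |
| 0.5 | Covariate | 5.7% | 8.0% | 11.9% |
| 0.7 | Change score | 8.8% | 20.7% | 40.2% |
| 0.7 | Covariate | 7.2% | 13.9% | 25.5% |
| 0.8 | Change score | 10.7% | 28.7% | 55.4% |
| 0.8 | Covariate | 9.1% | 21.8% | 42.4% |

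These rates are for one composite. Adjusting for baseline reduces the distortion but does not remove it.

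**5. Losses before baseline (assumed 5% to 10%).** 0.05 × 80 = 4 and 0.10 × 80 = 8 TBI participants. In power terms the cost is small: 38 per arm gives 85.3% and 36 per arm gives 83.4%, against 87.1%. The issue is randomized people with no data, not sample size.

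**The case against.** The strongest reply is that bias in the baseline needs someone who both knows the arm and can influence the score, and the documents show no such person. The coordinator's role in Section 7 is coordination and scheduling. The same section gives assessment administration and scoring to research technicians, and Section 10 states that the study technician is blinded. Supervisors review scoring, and data entry is verified. If every assessor is in fact blinded, randomizing before baseline does not by itself bias the baseline. That stands, and it limits the point to an exposure. It does not close it, because Section 7 also assigns the battery to Core psychometricians whose blinding is unstated.

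A reader might infer that injury severity could be called moderate more often in one arm. The documents do not support that: the facts behind severity are historical and are checked for eligibility before consent. The NSI is likewise first given at screening.

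A reader might also infer that losses before baseline will differ by arm. Participants are blinded, so that would need the coordinator to act on the assignment, and nothing shows this. Section 11 plans to examine missing-data patterns, although people with no observations contribute nothing to such an analysis.

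Finally, Section 10 refers to a design diagram that is not in the text available here, so the visit sequence was checked only against the written procedures. Those state the order twice.

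**Conclusion.** The point holds as an unprotected exposure in the starting half of the primary endpoint, and in the baseline BDI-II, HAM-D and WTAR, together with a route to randomized participants who have no data. The order of events and the coordinator's knowledge of the arm are explicit in the text.

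The size cannot be estimated from the documents. They give no dropout rate, no alpha, no pre-post correlation and no evidence of any baseline shift. The 7% to 26% range, or 6% to 12% with a baseline covariate, assumes ρ = 0.5 and a shift of 0.1 to 0.3 SD. It shows what a small leak would do and is not this trial's error rate. The 4 to 8 losses likewise rest on an assumed 5% to 10%.

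A reader might infer that the baseline is taken by people who know the arm. The documents do not say so. The case for change is that the protection is cheap and nothing in the plan requires allocation at consent.

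**What to change.** In Sections 10 and 18, replace the sentence "Randomization will occur at time of consenting" with wording to this effect: allocation is generated and revealed only after consent, confirmed eligibility, and a completed and locked baseline EXAMINER, BDI-II, HAM-D, WTAR, PROMIS-29 and NSI (and baseline EEG or MRI where done), just before the first stimulation session. Reorder the sentence that follows in each section to match.

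Add that staff who give or score assessments, at every visit, are blinded and are separate from the coordinator and from whoever programs the devices. Moving allocation alone would leave the post-treatment scores exposed. Reconcile the statement that the stimulator randomizes with the coin toss.

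The cost is a short amendment with no added visit. Device programming must fit between the end of baseline and the first session; the same-day or next-day window in Section 10 permits this, though one to two hours of EEG recording or 1.5 hours of MRI would make the same-day option tight for participants who have them. People who leave before baseline would be reported as pre-randomization exclusions. If 80 is to mean 80 randomized TBI participants, the assumed loss implies consenting about 85 (80 / 0.95 = 84.2) to 89 (80 / 0.90 = 88.9). If consent stops at 80, the number with baseline data is the same as under the present plan.

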*Established expertise in neuroimaging of TBI.* Our group has also been very active in the longitudinal study of TBI patients, utilizing multimodal neuroimaging and neuropsychological testing to assess biomarkers of injury and recovery. In adult and pediatric mTBI populations we have documented deficits in attention, post-traumatic symptoms, diffusion tensor abnormalities, neurometabolites, and fMRI differences, both in the semi-acute phase and in the chronic phase (4 months post-injury). We have used fMRI to examine attentional dysfunction in patients with TBI, observing decreased activation in both sub-cortical and cortical networks. The PI of this project has been providing clinical care for brain injured patients on an inpatient neurosurgical service and in an outpatient neuropsychiatry clinic for the past five years, and has ample experience with retention, characterization, and treatment of this clinical population. MRI sequences for characterization of TBI may be obtained as part of baseline and post-stimulation assessment in a subgroup of mmTBI subjects. The advantage of obtaining neuroimaging in this study is three-fold: 1) structural abnormalities may affect current flow and alter the effectiveness of TDCS; 2) TDCS has been shown by our group to increase glutamate under the anodal electrode, and use of MRS to characterize neurometabolite flux before and after stimulation could add important evidence to this theory; 3) mmTBI may cause functional brain activation abnormalities independent of structural lesions that can be correlated and localized with EEG.

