*Magnetic resonance imaging:* MRI scan(s) will involve simultaneous functional or cognitive tasks, including sequences assessing diffusion tensor imaging (DTI), magnetic resonance spectroscopy (MRS), functional MRI (fMRI), and structural sequences. Total scan time, including participant setup and removal, is expected to take 1.5 hours. Based on the study by Gasparovic et al in 2009 examining MR spectroscopy in mild TBI, utilizing an effect size of 1.27, a planned sample size of 30 subjects receiving MRI will achieve 80% power to detect a difference between groups. Participants may lie down on a table and be placed into a long donut-shaped magnet. During the scan, participants will be shown pictures and/or words and will be asked to make decisions about the information presented in them. No contrast will be used. Any female over 18 who thinks she may be pregnant will complete a urine pregnancy screen before the MRI scan. Results of pregnancy screens will be kept strictly confidential as per MRN policy. Urine samples will be disposed of immediately after testing.

*Left DLPFC anodal tDCS Intervention:* On the same day as assessment or the next day, participants will receive either active left anodal tDCS for a total of 30 minutes or sham for an equivalent duration, each day for up to ten consecutive weekdays. Current will be ramped up over 1 minute at initiation and ramped down over 1 minute with termination.

A NeuroConn tDCS (investigational) machine will be used to administer tDCS current. Targeting of the left DLPFC (F3 position, International 10-20 system of EEG coordinates) may be done by (1) locating the vertex (Cz) at the midpoint of the nasion-ion line and the midpoint of the preauricular-preauricular line; (2) locating M1 at 20% of the Cz-preauricular distance, measured from Cz; (3) locating F3 5 centimeters anterior to M1 in the horizontal plane. This method has been shown to be suitable for tDCS electrode targeting of left DLPFC. The Beam F3 method may also be used, which yields equivalent or better accuracy. Square-shaped solution-soaked or gel-soaked sponge electrodes, held by a rubber casing, are applied to the scalp using elastic bandage material. The anode will be placed on the scalp over the F3 target location and the cathode placed on the right upper arm

PROTOCOL TITLE: Transcranial direct current stimulation for treatment of deficits after traumatic brain injury.

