## **15. Data and Specimen Banking (see section on Data Management)**

## **16. Risks to Subjects**

Participation in this study for both healthy controls and mmTBI subjects may involve minor risks and/or discomforts associated with possible breach of confidentiality risk, neuropsychological testing, MRI, EEG, and tDCS.

**MRI:** Radio and magnetic waves associated with MRI scans are not associated with any known adverse effects. MRI is non-invasive and considered minimal risk by the FDA and OHRP. However, the scanner is a large magnet, so it could move objects containing ferrous metal in the room during the scan. All control and mmTBI participants are screened using the MRI safety screening form prior to being scanned. Participants with any MRI scanning contraindications will be excluded from study participation. Participants may be bothered by feelings of

**PROTOCOL TITLE:** Transcranial direct current stimulation for treatment of deficits after traumatic brain injury.

claustrophobia (uncommon). The MRI also makes loud ‘drum’ beating noises during the study. Headphones are provided for protection. Rarely, large or recent tattoos can heat up during an MRI scan and cause skin irritation like a sunburn (uncommon). No long-term harmful effects from MRI are known. However, since the effect of MRI on early development of the fetus is unknown, participants who are pregnant will not be allowed to go in the MRI. Females 18 years of age or older who suspect they may be pregnant will be asked to take a urine pregnancy test before being allowed to participate in the study. The test results will only be shared with participant.

**Neuropsychological tests.** The neuropsychological tasks involved in the protocol entail no foreseeable risk, besides perhaps fatigue or mild to moderate demands on attention and cognition. These are typically very marginally significant risks, mitigated by the fact that if a patient fatigues during testing they are given a rest break or are rescheduled. There is also mild psychological risk inherent in testing participants for cognitive abilities.

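### The 80% power stated for the 30-participant MRI subset is not shown for change after active versus sham stimulation, and does not reproduce from its own inputs

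*Combined protocol and SAP*

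**What the plan says.** The only sizing of the MRI subset is in Section 10, Magnetic resonance imaging. It refers to a 2009 spectroscopy study in mild TBI and states: "utilizing an effect size of 1.27, a planned sample size of 30 subjects receiving MRI will achieve 80% power to detect a difference between groups". It does not name the groups, the metabolite, the brain region, the time point, the test or the alpha level. No 2009 spectroscopy study appears in the reference list.

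The endpoint is in Section 5, where the secondary list includes "change in MRI abnormalities". Timing and population are in Section 2, under the neuroimaging expertise paragraph: "MRI sequences for characterization of TBI may be obtained as part of baseline and post-stimulation assessment in a subgroup of mmTBI subjects". That paragraph gives three reasons for imaging: structural lesions that may alter current flow, neurometabolites before and after stimulation, and functional abnormalities to be related to EEG.

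Section 16 (MRI) seems to cast the net wider: "All control and mmTBI participants are screened using the MRI safety screening form prior to being scanned".

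The only effect size that the plan assumes for active versus sham is d = 0.7, in Section 11, and it is derived from tDCS effects on cognition.

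**The concern.** A power figure belongs to one contrast on one outcome. Here the outcome listed is a change, the scans are taken before and after stimulation, and the trial randomises to active or sham. The between-group question for that endpoint is whether change differs by arm. The value 1.27 is not linked to any of this. As far as the text shows, it describes spectroscopy in mild TBI with no stimulation mentioned. A standardised difference in change also has a different denominator (the SD of change) from a difference at a single time point, so a value cannot be carried from one to the other without further argument.

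At stake is how the MRI result will be read. A reader told that the subset has 80% power would naturally attach that figure to the listed change endpoint and give a null result more weight than the design has been shown to support. The primary analysis is not affected.

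**Working it through.** **Inputs**
- N = 30 and effect size 1.27, read as Cohen's d; stated power 80% (Section 10, Magnetic resonance imaging).
- Equal split, 15 versus 15: assumed from the equal active and sham groups in Section 10, Participants.
- Two-sample t-test: assumed, as in the main calculation in Section 11.
- Two-sided alpha 0.05: assumed; the documents state none.
- All 30 have both scans: assumed; no loss rate is given.

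**Formula.** Noncentrality λ = d × √(n₁n₂/(n₁+n₂)), with n₁+n₂−2 degrees of freedom. Power is the probability that a noncentral t with parameter λ falls beyond the two-sided critical value.

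**1. The plan's own figure.** For 15 versus 15, √(225/30) = 2.739, so λ = 1.27 × 2.739 = 3.48 on 28 degrees of freedom. Power is 91.9% (93.6% by the normal approximation; 96.0% one-sided). The stated 80% does not reproduce. This holds whether the two groups of 15 are active and sham or TBI and healthy.

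**2. What would give about 80% at d = 1.27**
- 11 per group: λ = 1.27 × √(121/22) = 2.98, power 80.9%. That is 22 participants, or a loss of 8/30 = 27%.
- Alpha 0.05/3 with 15 versus 15: power 81.7%.

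Neither assumption is stated.

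**3. Active-versus-sham change, 15 versus 15.** The documents give no tDCS effect size for any MRI measure, so a range is shown:

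| d (illustrative) | λ = 2.739 × d | Power |
|---|---|---|
| 0.5 | 1.37 | 26% |
| 0.7 | 1.92 | 46% |
| 1.0 | 2.74 | 75% |
| 1.06 | 2.90 | 80% |

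The smallest effect detectable with 80% power is d = 1.06. For scale, 80% power at d = 0.7 would need 34 per arm, 68 in all.

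**4. If half of the 30 were healthy controls.** No split is given in the documents, so this is a what-if. About 15 TBI participants, 8 versus 7, give √(56/15) = 1.932. Within-TBI power is then 15% at d = 0.5, 24% at d = 0.7, 43% at d = 1.0 and 62% at d = 1.27. The detectable effect at 80% power is d = 1.57.

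**The case against.** The strongest defence is that "to detect a difference between groups" may mean TBI versus healthy. Section 2 (Choice of study population) recruits controls partly to show deficits in TBI, the sequences are described as characterising TBI, and Section 16 contemplates scanning controls. A spectroscopy effect size in mild TBI would be a natural source for such a baseline comparison. This reading is open, and it stands. It does not rescue the sentence, because the listed change endpoint is then left without any power statement.

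It is also true that no section writes the MRI contrast out as active versus sham. Section 11 names EEG and the Examiner composites for that comparison and leaves the imaging analysis open. The contrast is inferred from the randomisation, the change endpoint and the scan timing.

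Four stronger readings are tempting, and the documents do not support them:
- That 1.27 is proven to be the wrong contrast. The source study's comparison is not described and cannot be verified here.
- That the subset's true power is 46% or 24%. The value d = 0.7 is a cognitive benchmark, and applying it to imaging as an estimate would repeat the borrowing at issue. The 8-versus-7 split is hypothetical, and an analysis pooling TBI participants and controls could still compare 15 with 15.
- That a null MRI result would count as refuting the glutamate mechanism. MRI is optional throughout, and Section 2 says only that spectroscopy could add evidence.
- That the endpoint should become glutamate alone and that controls should not be scanned. Section 2 gives three imaging rationales, and both changes would be scientific preferences.

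**Conclusion.** The point holds in limited form. The 80% is not supported for active-versus-sham change, because its effect size is not tied to stimulation or to change and the groups are unnamed. Under the alternative reading, the change endpoint has no stated power.

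Separately, the figure fails to reproduce: 92% against 80%, under an equal split and a two-sample t-test at two-sided 0.05. A reader might infer that the plan inflates its power. On its own inputs it understates it, so the arithmetic error is in the conservative direction. The main issue is which effect the figure refers to.

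What can be said firmly is that 15 versus 15 with complete scan pairs detects d = 1.06 with 80% power. Power at any smaller effect depends on an assumption that the documents cannot supply. The matter concerns one secondary endpoint and should be corrected; it does not threaten the trial's main conclusion.

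**What to change.** Keep the 30 participants and replace the power sentence in Section 10, for example with:

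> 30 TBI participants (15 active, 15 sham) give 80% power to detect d = 1.06 in pre-to-post change (two-sided 0.05, two-sample t-test). Power is about 26% at d = 0.5, 46% at d = 0.7 and 75% at d = 1.0; these values are illustrative, as no MRI-specific tDCS effect size is available. The MRI comparison is exploratory.

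Reconcile Section 2 (a subgroup of TBI participants) with Section 16 (controls and TBI participants) on whether the 30 include healthy controls. If they do, give the split and the lower within-TBI power; at 8 versus 7 the detectable effect is d = 1.57. If a TBI-versus-healthy comparison was meant, name it and its source contrast, and give it a power statement separate from that for change.

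The cost is wording only, with no added participants or scans. The downside is a less favourable stated power.
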